5. TREATMENT OF SUBJECTS

Not applicable

6. INVESTIGATIONAL PRODUCT

Not applicable

7. NON-INVESTIGATIONAL PRODUCT

Not applicable

8. METHODS

8.1 Study parameters/endpoints

The COPP-IMM study is closely related to the ongoing observational clinical cohort study COPP (N20.043). The COPP-IMM study consists of two parts:

- a) a clinical cohort study, identical to the COPP-study (the data of children included in COPP-IMM will be analysed together with the data of children included in the COPP-study). A summary of this analysis is shown on the website <https://covidkids.nl/scientific-dashboard/>
- b) detailed immunological profiling, in relation to clinical phenotype

As of April 2021, 53 hospitals are participating in the COPP study. When the COPP-IMM study starts, 17 of these will participate in the COPP-IMM study instead of the COPP study. The remaining 36 hospitals will continue to participate in the COPP study. Clinical data from COPP and COPP-IMM will be collected using the same database (using eCRFs in Castor) and will be analysed as one dataset.

For the COPP-IMM study, patients/parents/guardians can choose if they wish to participate in:

- Only the clinical observational part of the study, with or without questionnaires (similar to the COPP-study)
- Both the clinical observational part of the study **AND** the immunological part of the study (one blood sample at diagnosis)

8.1.1 Main study parameter/endpoint

For the clinical observational part of the study (analyzed together with data from the COPP-study) the main study parameters are:

- To describe the clinical features of the COVID-19 in hospitalized and outpatient pediatric patients in the Netherlands.
- To describe the clinical course of the COVID-19 in hospitalized and outpatient pediatric patients.
- To describe the response to treatment, including supportive care.
- To determine risk factors for severe disease in children with COVID-19.

For the immunological part of the COPP-IMM study, we will obtain a detailed immunological profile of children presenting to Dutch hospitals with acute SARS-CoV-2 infection or with a SARS-CoV-2 related post-infectious inflammatory syndrome. Since clinically relevant pediatric COVID-19 is rare and we will have a limited amount of material available from each patient, we will do this in a two-tiered approach. This will enable us to choose which will be the most informative in-depth immunological analysis following a more general screening of the innate and adaptive immune system.

In the FIRST TIER we will do a general assessment of the immune system. In this general assessment we will do the following investigations:

1. Detailed phenotypical analysis of the cells of the innate and adaptive immune system using multicolor flow cytometry. We will use the EuroFlow protocol PID Orientation

tube to be able to identify and quantify the main leukocyte and lymphocyte subsets, using 12 markers: CD27, CD45RA, CD8, IgD, CD16, CD56, CD4, IgM, CD19, CD3, CD45, and TCR $\gamma\delta$. This will enable us to identify B-cells (including B-cell subsets), T-cells (including T-cell subsets), NK-cells, monocytes (including non-classical CD16+ monocytes), dendritic cells, basophils, neutrophils and eosinophils (minimum of 4 mL of EDTA needed).

2. Multiplex analysis of inflammatory cytokines in serum using Luminex bead arrays (in excess of 100 analytes, to determine Th1/Th2 and innate responses) (200-400 uL).
3. Quantitative and qualitative (affinity) analysis of anti-SARS-CoV-2 antibodies in serum and potential cross-reactive antibodies to other coronaviruses (200-400 uL).

Depending on the results of the investigations in the first tier, we will choose one of the following in-depth immunological analyses for the SECOND TIER:

[figure not shown]
1. The innate immune system (whole blood stimulation assays with cytokine production, single cell RNAseq or advanced flow cytometric phenotyping of the innate immune system).
2. The adaptive immune system; with either a focus on T-cell responses (T-cell stimulation assays to evaluate effector responses against SARS-CoV-2 peptides), or B-cell responses (in-depth B cell subset analysis).
3. Biomarker discovery of serum proteins using multiplex assays such as Olink or mass spectrometry.

In almost all children we expect to be able to perform all analyses from the FIRST TIER, even in the youngest children (4 mL of EDTA-blood and 1 mL of blood in serum tube). For the analyses in the SECOND TIER, we will have to prioritise the analyses, especially in those patients for whom only a limited amount of blood is available. The exact priority of analyses in the SECOND TIER depend on the results obtained in the FIRST TIER.

Examples:

- If FIRST TIER analysis will demonstrate marked changes in CD4/CD8 T cell distributions in children with severe COVID-19 as compared to non-severe COVID-19, the SECOND TIER investigations will focus on detailed T cell analysis (advanced T cell phenotyping and functional assays) in children with severe and non-severe COVID-19.
- If FIRST TIER analyses show high levels of cytokines associated with inflammasome activity (IL-1beta, IL-18) in children with MIS-C as compared to children with COVID-19, the SECOND TIER analysis will focus on *in vitro* stimulation of monocytes with inflammasome activating agents and in-depth innate immune phenotyping in children with MIS-C and COVID-19.

If less than 2×10^6 mononuclear cells are isolated from the EDTA blood sample, then these will not be used for flow cytometry in the FIRST TIER, but will be stored to be used in SECOND TIER analyses that require small amounts of cells (such as single cell RNA sequencing).

8.1.2 Secondary study parameters/endpoints (if applicable)

We will correlate the immunological profiles with detailed clinical outcome measures of the patients. We will collect these clinical outcome measures in the same manner as in our related cohort study 'Clinical features of COVID-19 in Pediatric Patients' (COPP-study). Clinical parameters collected include: severity of disease (need of supplemental oxygen); underlying illnesses; age at presentation; clinical syndrome; laboratory parameters at diagnosis and during illness; response to treatment; clinical outcome: days of hospitalization, life-saving interventions, ICU admissions, death, patient reported outcome measures at 6 weeks follow-up.

Also, we will explore if there are potential immunological targets of therapy for children with severe COVID-19 or MIS-C, and if immunological profiles differ between MIS-C and severe pediatric COVID-19.

8.1.3 Other study parameters (if applicable)

Immunological analyses will be done in cooperation with research-teams investigating adult patients with COVID-19 (eg in the BEAT-COVID1 study), so as to be able to compare hospitalized children and adults with COVID-19. Also, where possible, immune responses in hospitalized children will be compared with results from pediatric population-based studies.

We will perform similar immunological analyses in children included in the follow-up study COPP-2 (multi-center study in which children included in the COPP-study will be invited 6-12 months after presentation for a multi-disciplinary follow-up assessment).

The PedsQL and TAPQOL questionnaires measure Health Related Quality of Life at 12 weeks after diagnosis. To measure overall health and specific domains of functioning (anxiety, depression, peer relationships, sleep problems, anger, and neurocognitive functioning, anger and fatigue), we will use the PROMIS items in children older than 8 years of age. Patients admitted to the intensive care unit undergo neuropsychological evaluation as standard care in most Dutch academic centres, 3-6 months after admittance to the intensive care unit. We ask parents and patient for permission to retrieve these results.

The outcome of these psychosocial and Quality of Life evaluations will be analysed together with the detailed clinical parameters of our participants in the COPP and COPP-IMM study to examine possible risk factors for reduced quality of life or neuropsychological outcomes after COVID-19 or MIS-C.

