8.2 Randomisation, blinding and treatment allocation

not applicable

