10. STATISTICAL ANALYSIS

10.1 Primary study parameter(s)

Statistical analysis of the primary objective: immunological profiling of children with COVID-19 or MIS-C:

1. Relative distributions of immune cell subsets will be obtained by multicolor flow cytometry. Data will be imported in R for statistical analysis. Cytosplore will be used for clustering and dimensionality reduction (9). Distributions will be compared to available reference values (normal distribution of immune cell subsets in children, adjusted for age) and will be compared across subgroups (mild COVID-19, moderate to severe COVID-19 and MIS-C).
2. Cytokine levels will be analyzed in R and SPSS. Levels will likely be non-normally distributed, in which case non-parametric Kruskal-Wallis tests will be done for comparison across groups. To adjust for multiple testing, we will use the two-stage step-up method of Benjamini *et al* (10). Cytokine levels will be compared to normal values as already available for healthy adults, and across the subgroups(mild COVID-19, moderate to severe COVID-19 and MIS-C).
3. Levels of neutralizing antibodies will be compared across subgroups (mild COVID-19, moderate to severe COVID-19 and MIS-C) using ANOVA in SPSS.

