10.3 Other study parameters

Comparison between immunological profiles of hospitalized children with COVID-19 and other cohorts (eg adults with severe COVID-19, non-admitted children with COVID-19) will be done using parametric (ANOVA) or non-parametric (Kruskal-Wallis) tests were applicable, depending on whether the data is normally distributed or not. Logistic regression will be used to determine associations between clinical parameters and the results from the questionnaires on Quality of Life and functioning.

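### Section 10.3 plans significance tests of this cohort's immune profiles against other cohorts without requiring a shared or linked assay, so for comparators measured elsewhere a laboratory difference can pass as an immune difference.

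*Protocol*

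**What the plan says.** Section 8.1.3 of the protocol plans two kinds of external comparison.

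- **Adults:** "Immunological analyses will be done in cooperation with research-teams investigating adult patients with COVID-19", with the stated purpose of comparing hospitalised children and adults.
- **Other children:** "where possible, immune responses in hospitalized children will be compared with results from pediatric population-based studies".

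Section 10.3 gives the method. It covers "Comparison between immunological profiles of hospitalized children with COVID-19 and other cohorts", names adults with severe disease and non-admitted children as examples, and uses ANOVA or Kruskal-Wallis where applicable, according to whether the data are normal. It does not mention laboratory, assay run or common control samples.

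Section 10.1 also brings outside values into the primary analysis. For cytokines, "Cytokine levels will be compared to normal values as already available for healthy adults". For cell subsets, "Distributions will be compared to available reference values (normal distribution of immune cell subsets in children, adjusted for age"). It names no specific test for these reference comparisons.

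The cytokine panel in section 8.1.1 has more than 100 analytes. Section 10.1 sets a two-stage step-up false-discovery procedure for cytokines. Section 10.3 states no multiplicity method.

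**The concern.** ANOVA and Kruskal-Wallis ask whether two sets of measurements differ. They cannot tell why. If all the children's samples are measured in one laboratory or set of runs and all the comparator samples in another, any difference in calibration, reagent lot, instrument setting or gating enters in full as a difference between cohorts. Adding a laboratory term would not help, because that term would be identical to the cohort term.

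False-discovery control does not help either. It limits the share of rejections that arise by chance when there is no difference in the measurements. A laboratory shift is a real difference in the measurements, only not a biological one.

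What is at stake is the reading of the external comparisons. A statement that hospitalised children differ from the general paediatric population, or from adults, could rest on where the samples were measured.

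**Working it through.** **The plan's own figures.** Section 4.1 expects about 60 children, with consent for blood sampling in about half: 60 × 0.5 = 30. Section 4.4 splits these as 10 + 10 + 10 = 30. The figure reproduces. No power or effect-size figure exists to check.

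**Inputs.**
- Children with immune profiles: 30 (sections 4.1 and 4.4).
- Comparator size: not in the protocol. Assumed 30, with 100 as an alternative.
- Significance level: not stated. Assumed two-sided 5%.
- Within-group SD: set to 1.
- Between-laboratory shift per analyte: not in the protocol. Assumed random with mean 0 and SD *s* of 0.3 to 0.5. Fixed shifts are also shown.
- True immune difference: none.

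**Error per analyte, random shift.** The observed mean difference has variance se² + s², while the test judges it against se alone:

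error = P(|N(0, se² + s²)| > 1.96 se), with se = √(1/n₁ + 1/n₂).

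For 30 v 30, se = √(2/30) = 0.258 and the threshold is 1.96 × 0.258 = 0.506.

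- s = 0.3: √(0.0667 + 0.09) = 0.396; 0.506 / 0.396 = 1.28; error = **20%**.
- s = 0.5: √(0.0667 + 0.25) = 0.563; 0.506 / 0.563 = 0.90; error = **37%**.

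For 30 v 100, se = √(1/30 + 1/100) = 0.208 and the threshold is 0.408.

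- s = 0.3: 0.408 / 0.365 = 1.12; error = 26%.
- s = 0.5: 0.408 / 0.542 = 0.75; error = 45%.

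A larger comparator makes matters worse, because the chance error shrinks while the laboratory shift stays.

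**Error per analyte, fixed shift (simulated Kruskal-Wallis).**

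| Shift (SD) | 30 v 30 | 30 v 100 |
|---|---|---|
| 0 | 5% | 5% |
| 0.25 | 16% | 22% |
| 0.5 | 45% | 63% |
| 1.0 | 96% | 99.8% |

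The zero-shift row is what a shared or properly linked assay would give.

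**After false-discovery control.** Simulation of 100 independent analytes, 30 v 30, with no true difference, analyte-specific shifts and the two-stage step-up procedure at 5%. Mean number of analytes declared different:

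- no shift: 0.04
- s = 0.3: about 4
- s = 0.5: about 24
- s = 1.0: about 63

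So the procedure named in 10.1 would not protect these comparisons even if it were carried over to 10.3.

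**The case against.** **The protocol hedges, and part of the work is joint.** The paediatric comparison is made only where possible, and 10.3 applies its tests only where applicable. The adult work is done in cooperation with the adult teams so that a comparison can be made. This stands in part. Cooperation may well mean a shared assay, and confounding is then not established for adults. But the protocol does not say so, the cooperation sentence does not cover the paediatric population studies, and the only stated basis for choosing a test is normality.

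**These are other parameters in an exploratory study, and the comparator size is not given.** Both are true. They limit the weight of the point and make the percentages illustrative. They do not make a confounded test interpretable.

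**Descriptive reporting leaves the shift in place.** This is correct, so the fix also asks that such comparisons be labelled as confounded with laboratory.

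**Stronger readings that the protocol does not support.**

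- *That comparisons between the study's own groups are equally distorted.* A reader might infer this from 18 to 36 months of collection and from MIS-C arising some weeks after infection. Nothing says that samples are assayed in order of arrival or that groups fall into different runs. In simulation with 10 per group and 20%, 50% and 80% of the groups in the second of two runs, a fixed run shift of 0.5 or 1 SD gave 6% or 12% error. With analyte-specific shifts of SD 0.5 or 1, false-discovery control left under 0.05 false findings per 100 analytes. With MIS-C wholly in its own run the effect can be large (15% and 53%; 0.9 and 29 per 100 after control), but no text sets up that layout.
- *That the study rejects masked laboratory reading.* The entry under "Randomisation, blinding and treatment allocation" is not applicable, which is a correct answer for a study that allocates no treatment. It says nothing about laboratory masking. Plate layout and gating rules commonly sit in a laboratory procedure or analysis plan that is not shown.
- *That the choice of second-tier assays rests on the external comparisons.* Both examples in section 8.1.1 are contrasts within this cohort.

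**Conclusion.** The point holds for external comparators that were not measured on the same runs or linked by shared controls. The protocol fixes the comparator (8.1.3) and the tests (10.3) without that condition, so a significant result cannot be assigned to cohort rather than laboratory.

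The confounding follows from the design and needs no assumption about size. The size does: the range of 20% to 37% rests on an assumed comparator of 30 and an assumed shift SD of 0.3 to 0.5, neither of which is in the protocol. A smaller shift would do less harm, and a larger shift or a larger comparator more.

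For adults the conclusion is conditional on whether the cooperation includes a shared assay. For the reference values in 10.1 the same logic applies to any formal test, although none is specifically named there. The point is worth correcting because it changes what the external comparisons can show. It does not bear on the comparisons among mild COVID-19, moderate to severe COVID-19 and MIS-C.

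**What to change.** In section 10.3, state that formal tests against other cohorts are limited to cohorts whose samples were measured on the same runs as the study samples, or linked to them by shared control samples. Report all other external comparisons descriptively, without p-values, and describe them as confounded with laboratory. Apply the same rule to the healthy-adult cytokine values and the cell-subset reference values in 10.1. In 8.1.3, say whether the cooperation with the adult teams includes a shared or linked assay.

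This takes a few sentences and no extra patients or blood from the children. The downside is fewer significance tests against outside cohorts. Where a formal test is wanted, the cost is arranging joint runs or exchanging control samples. Balancing plates by clinical group is at most an optional suggestion for the laboratory procedure and is not part of this correction.

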8.2 Randomisation, blinding and treatment allocation

not applicable

8.3 Study procedures

1. **Patients will be included** in the study in case of SARS-CoV-2 positive test, or fulfilling a clinical diagnosis of COVID-19, or fulfilling a diagnosis of MIS-C; and after obtaining informed consent (IC) from both guardians and/or patient. Because only one parent can accompany the hospitalized child (due to COVID-19 restrictions), initially it is only one guardian who will sign the consent form. If applicable, the signature of the second guardian will be collected as soon as possible. Consent can be given for just the clinical part of the study (with or without consent for follow-up studies); or for both the clinical and immunological part of the study.
2. **Clinical data** from the subject at time of presentation in the hospital will be noted in a case report form. In case of a diagnosis of COVID-19 after hospital presentation the data will be collected from the electronic medical record. Summarized this data will contain:
 - a. Patient characteristics and risk factors: age, gender, height, weight, exposure to known COVID-19 cases, prior medical history, medication.
 - b. Clinical features at presentation: symptoms, vital signs, physical examination, imaging results, laboratory results.
 - c. Course of illness: clinical symptoms, vital signs, physical examination, imaging results, laboratory result, the need for respiratory support, the need for IC treatment, medication, aerosol treatment, co-morbidity and outcome.Clinical data will be recorded in Castor. For details regarding the datamanagement plan see **Appendix A**.

When patients are being admitted to the IC, additional information about the neurological tests that have been performed (standard care) will be collected for

this study. Guardians and/or children can give consent for this data collection in our standard consent form.

3. **Blood samples** for this study will be collected after confirmation of the diagnosis COVID-19 or MIS-C and after the patient and/or the caregiver have consented for participation in this study. If possible, the collection of the blood sample will be combined with a blood sample collection for routine clinical care and/or will be drawn from an indwelling venous catheter. In this case, there will be no additional burden to the patient.

If after confirmation of the diagnosis and obtainment of informed consent, no blood sample collection is scheduled for routine clinical care and there is no venous catheter present from which the blood can be drawn, a venepuncture will be done to collect material for this study. In this case, there will be some burden to the patient. To ensure that this burden is minimal, we will apply a topical anaesthetic (lidocaine/prilocaine or lidocaine/tetracaine as per local guidelines) prior to the procedure. Also, we will instruct local researchers to engage in “positive language” before and during the procedure (See **Appendix B**).

The amount of blood drawn depends on the body weight of the patient. With these amounts, we remain well below the recommended maximum of 3% of total blood volume in all weight categories (8). If the local investigator does not succeed in obtaining the required amount of blood, a smaller sample will be collected. In that case, immunological investigations will need to be prioritized (see 8.1.1 for details regarding priorities).

body weight	EDTA (mL)	serum (mL)	total volume (mL)
3-5 kg	4	1	5
5-10 kg	5	2	7
10-20 kg	10	5	15
20-40 kg	20	10	30
>= 40 kg	30	10	40

Scarce material from blood samples will be stored in local centers. They will be used to retrospectively analyze additional laboratory parameters associated with severity of disease and outcome, such as cytokine levels (particularly IL-6) and medication concentrations (particularly chloroquine).

4. **Timing of sampling**

We aim to collect the sample *as soon as possible* after inclusion in the study, preferably before any *immune modulatory medication* has been administered. This will enable us to determine the immunological profile in the *acute phase* of the illness. The acute phase of the illness is defined as: at presentation of the patient (in case of screening, asymptomatic patient or ambulatory patient) OR ongoing symptoms (in case of acute COVID-19) OR ongoing signs of hyperinflammation (in case of MIS-C). The local investigator will note the exact date and time of blood sampling in the case report form.

For a Standard Operating Procedure regarding the blood draw and logistics, see **Appendix C**.

5. If available, locally **stored samples** will be collected to retrospectively analyze the immunological parameters of the patients in this study, particularly if no consent was obtained for additional sampling for the COPP-IMM study, if an extra blood draw was not feasible for logistic reasons, or if longitudinal analyses are informative.
6. **Follow-up questionnaire** at 12 weeks after start of symptoms (See **Appendix D**). The questionnaires are age-appropriate and contain the following topics: general complaints, remaining symptoms, recovery to normal life, overall health, and quality of life using validated surveys: PedsQL (Pediatric Quality of Life Inventory) and PROMIS (Patient-Reported Outcomes Measurement Information System). PROMIS outcomes are: anxiety, depression, anger, peer relations, sleeping problems, overall health and fatigue. These surveys have been evaluated by the patient support group (Kind & Ziekenhuis). The flow diagram of the follow-up surveys is displayed in **Appendix E**.
7. A separate 2 minutes questionnaire will be sent to children eligible for vaccination against SARS-CoV-2. This questionnaire consists of questions about if a child was vaccinated, and if so, when and if there were any side effects. We will send this questionnaire once a year during the course of this study.

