4.3 Exclusion criteria

A potential subject who meets any of the following criteria will be excluded from participation in this study:

- No evidence of current or recent COVID-19
- No consent from guardians and/or patient
- For the blood sampling: body weight less than 3 kg.

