4.4 Sample size calculation

A formal sample size calculation cannot be done, since it is currently unknown what the variation in immunological response is children with COVID-19 or MIS-C and how this relates to outcome measures. Based on the number of participating sites and the inclusion rate in the first wave of the epidemic, we expect to be able to include at least 60 children in total, and 30 children for the immunological part of the study.

We expect the rate of consent for blood withdrawal to be higher in patients with more severe disease (since the blood can be taken during routine blood withdrawal and no separate venapuncture will be needed). Therefore, based on inclusion rates for the related COPP-study, we estimate we will be able to include at least 10 patients with MIS-C, 10 patients with moderate to severe COVID-19 and 10 patients with mild COVID-19. Clinical information will be available for all of the patients included in the immunological part of the study.

If we will have reached 60 inclusions for the immunological part of the study within the first 18 months of the study, we will do an interim analysis to determine if more inclusions are needed. Since this is an exploratory study, no formal maximal number of inclusions can be given, but based on previous inclusions in de COPP-study and the expected course of the epidemic we do not expect to reach a higher inclusion than 60 in this timeframe.

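### Section 8.3 item 5 provides for immunological analysis of stored samples without tying it to consent for the immunological part, and nothing keeps those samples apart in the subgroup comparisons

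*Protocol*

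**What the plan says.** Protocol section 8.1 offers two forms of participation. The first is "Only the clinical observational part of the study, with or without questionnaires (similar to the COPP-study"). The second adds "the immunological part of the study (one blood sample at diagnosis"). Section 8.3 item 1 repeats the split: "Consent can be given for just the clinical part of the study (with or without consent for follow-up studies"), or for both parts.

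Section 8.3 item 5 then deals with locally stored samples, which, if available, "will be collected to retrospectively analyze the immunological parameters of the patients in this study, particularly if no consent was obtained for additional sampling" for COPP-IMM. The same sentence gives two further triggers: "if an extra blood draw was not feasible for logistic reasons, or if longitudinal analyses are informative".

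Section 4.3 excludes children for "No consent from guardians and/or patient", without reference to stored material. Section 4.4 adds: "We expect the rate of consent for blood withdrawal to be higher in patients with more severe disease". The reason given there is that the blood can be taken at a routine draw, without a separate puncture.

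Section 10.1 compares cell subsets, cytokines and antibodies across mild COVID-19, moderate to severe COVID-19 and MIS-C. It says nothing about the source of a sample.

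**The concern.** There are two issues, and the first carries the weight.

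**Consent.** Measuring immunological parameters is what the immunological part consists of. Section 8.1 describes that part by its blood sample at diagnosis. Item 5 names the absence of consent for study sampling as a reason to do the same kind of measurement on material already in store, and does not require any other consent for immunological use. A site that follows item 5 literally would forward material from children whose families chose the clinical part only. These are minors in non-therapeutic research (section 11.4), and results obtained outside a family's choice might have to be withdrawn.

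**Comparability.** Two of the three triggers cover children for whom the study draw did not take place. Their stored samples may differ from study samples in tube, delay, storage and timing relative to treatment. Section 8.3 item 4 asks for the study sample as early as possible and preferably before immune-modulating medication. Item 5 sets no such condition. If source also differs between the three subgroups, a handling or timing effect could be read as a difference in immune profile.

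**Working it through.** **1. The plan's own figure.** Section 4.1 expects about 60 children and about 50% consent for blood withdrawal:

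60 × 0.50 = 30.

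This reproduces the stated 30, and it matches the subgroups in section 4.4: 10 + 10 + 10 = 30.

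**2. Children under the no-consent trigger.** 60 − 30 = 30. This is an upper bound on the stored samples arising from that trigger.

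**3. Share of profiles from this route.** Let *f* be the share of these 30 children with a usable stored sample. The protocol does not give *f*, so the values below are assumptions.

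Share = 30*f* / (30 + 30*f*)

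| *f* (assumed) | stored samples | total profiles | stored share |
|---|---|---|---|
| 0% | 0 | 30 | 0% |
| 10% | 3 | 33 | 9% |
| 25% | 7.5 | 37.5 | 20% |
| 50% | 15 | 45 | 33% |
| 100% | 30 | 60 | 50% |

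**4. Consent wording side by side.**

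- Sections 8.1 and 8.3 item 1 describe clinical only, or clinical plus immunological. Neither describes agreement to immunological use combined with refusal of an extra draw.
- Section 8.3 item 5 provides for immunological analysis where consent for study sampling is missing, for patients in the study generally.
- Section 4.3 requires some consent to be in the study. A clinical-only family meets that requirement, so the exclusion does not settle the matter.

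**5. Does source differ by subgroup?** Section 4.4 points both ways. Consent is expected to be lower in milder disease, so more mild cases would fall under the trigger. The reason given is that routine draws are available in more severe disease, so if the stored samples are routine left-overs, mild cases would less often have one. The net direction cannot be derived.

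**6. Would it matter?** As an illustration, keep the 10/10/10 study samples of section 4.4 (mild / moderate to severe / MIS-C). Add stored samples shifted by 0.5 or 1.0 SD, with no true group difference. Use normal data and Kruskal-Wallis at 0.05 (an assumed level; the protocol gives none), with 8,000 runs per setting.

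| stored samples added | rejection, 0.5 SD | rejection, 1.0 SD |
|---|---|---|
| 5/3/2 | 4.7% | 3.8% |
| 8/4/3 | 4.8% | 4.0% |
| 10/10/10 | 4.1% | 2.5% |
| 20/5/5 | 6.4% | 11.2% |
| 5/5/20 | 6.9% | 12.1% |

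With modest or balanced additions there is no inflation. It appears only when nearly all non-consenting children have a sample and these pile up in one subgroup. The shift and the splits are assumptions, so no row is an expected result.

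**The case against.** The strongest defence is that absence of consent for additional sampling, listed beside an infeasible extra draw, can mean refusal of another draw and not refusal of immunological use. The item covers patients already in the study. Section 11.2 refers to an attached information letter and consent form, which are not available here and may cover left-over material. This stands as far as it goes: one cannot conclude that the protocol overrides families' choices or that data will be obtained against them. It does not remove the conflict, because the protocol describes the choices twice and neither description contains that middle option.

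A reader might also infer that item 5 is aimed at non-consenting children. The documents do not support this: logistics and longitudinal analysis are triggers too, and both can apply to consenting families.

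On the analysis, a reader might infer that non-SOP routine samples are mixed into the section 10.1 tests. The protocol does not call the samples routine or non-SOP. Section 8.3 item 3 mentions local storage of blood material without stating its origin, and the content of the SOP in Appendix C is not shown. Section 10.1 neither includes nor excludes stored samples, and handling of sample source could properly sit in an analysis plan that is not at hand. Sampling date and time and medication are recorded, which partly covers timing. What remains is a risk left open, not a stated practice.

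**Conclusion.** The point holds as a conflict in consent scope that must be reconciled, with a secondary analysis risk.

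Up to about 30 of about 60 children could fall under the no-consent trigger. Stored samples from them could form 0% to 50% of profiles, depending on an availability rate that the protocol does not state. The upper end assumes that every non-consenting child has a usable sample.

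For the section 10.1 comparisons, the supported statement is that pooling is not prevented and that source may differ by subgroup, in an undetermined direction and size. Two stronger readings are tempting. One is that stored samples would be over-represented among milder children; this ignores the reason section 4.4 gives for higher consent in severe disease. The other is that false-positive rates would clearly exceed 5%; this needs near-complete availability and strong imbalance, neither of which the protocol implies. The false-discovery-rate adjustment planned for cytokines would not remove a source effect if there were one, but no expected magnitude can be given.

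**What to change.** 1. Reconcile section 8.1 and section 8.3 items 1 and 5. Either limit item 5 to children with consent for immunological use of their material, or describe a separate consent option for stored or left-over samples. If the consent form already has such an option, state it in the protocol.
2. Add an eCRF field for sample source (study draw or stored sample).
3. Report the section 10.1 comparisons with a sensitivity analysis that excludes stored samples.

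The cost is a protocol clarification, one eCRF field, a little extra analysis and possibly a few fewer samples. The planned 30 does not change, because section 4.1 derives it from consent to blood withdrawal alone.
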